6.2. EARLY TERMINATION

The vitamin D dosage used in this study is considered to be of a safe level for daily intake and is currently recommended as the AI for vitamin D in Australia. It is unlikely to cause any side effects or symptoms by obtaining this dosage level through sun exposure, dietary change or supplementary intake. However, some participants may experience allergy or food intolerance risks by adding seafood or eggs into their daily meals even if cleared from allergy history at the initial screening. Participants with any severe allergic reaction or food intolerance will be excluded from current study, relevant medical treatment including allergy test would be arranged for participants if necessary.

7. BLINIDING AND UNBLINDING

The study therapist blind to treatment allocation will conduct the baseline assessment/monthly assessment for the anthropometry, dietary and sun exposure data collection. The pathology technician who is blind to treatment allocation will conduct the blood test. Due to the nature of the intervention, neither participants nor assessors will be blinded to the intervention but will be informed not to disclose the allocation status or status of the participant at the follow-up assessments. An employee outside the research team will input data into the computer in separate datasheets so that the research team can analyse data without having access to information about the allocation.

8. STATISTICAL CONSIDERATIONS*

By setting the significance level α =0.05, the power 1- β = 0.8 based on Campbell & Machin (1993) formula: m=(Z α + Z2 β)2{ π 1(1- π 1)+ π 2(1- π 2)}/ δ 2, (Z α + Z2 β)2 = 7.849, δ = π 2- π 1=0.7-0.35= 0.35; therefore m=28. Therefore the sample size for each group in the current study was calculated to be

at least 28, with at least 112 in total. With the consideration of a dropout rate 10%-20%, it is planned to recruit 123-134 participants in total hence 31-34 participants for each group.

Data are expressed as means ± SDs. Initially, the Kolmogorov–Smirnov goodness-of-fit test will be used to assess the normal distribution of the values. Secondly, two-factor repeated-measures analysis of variance (ANOVA) with a Bonferroni correction will be used in the current trial with time stages and interventions as factors. Tukey's post-hoc comparison will be applied to identify the differences between four intervention groups at 3 months and 9 months in the case of significant interaction finding in ANOVA. Thirdly, correlations between variables will be evaluated by using either a Pearson (r) (for data with normal distribution) or a Spearman (rs) (for data with no normal distribution) correlation. A p-value <0.05 is considered to be statistically significant. All statistical analyses will be computed using the Statistical Package for Social Science version 17 (SPSS, Chicago, IL, USA). Missing values are to be treated according to the last observation carried forward (LOCF) method and will be assessed via sensitivity analysis.

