2. STUDY OBJECTIVES*

2.1. PRIMARY OBJECTIVE*

To determine the role of vitamin D (through vitamin D oral supplementation, sun exposure, dietary intervention compare to wait list control) in controlling and reducing DM risks (as measured by HbA1c).

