3.2. STUDY GROUPS

Eligible participants will be randomised in equal proportion into 4 groups: vitamin D supplement, dietary intervention, sun exposure and wait list control.

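### The stated 80% power is for one unadjusted comparison of two undefined proportions and is not shown for the planned four-arm analysis of mean HbA1c

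*Protocol*

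**What the plan says.** The sample size paragraph appears in the Synopsis, section 3.3 and section 8 with the same inputs.

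- Error rates: "By setting the significance level α =0.05, the power 1- β = 0.8".
- Multiplier: "Z α + Z2 β)2 = 7.849".
- Effect and result: "0.7-0.35= 0.35; therefore m=28. Therefore the sample size for each group".
- Total: "at least 28, with at least 112 in total".
- Dropout: "With the consideration of a dropout rate 10%-20%, it is planned to recruit 123-134 participants in total", which the protocol gives as 31-34 per group.

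On the endpoint, section 2.1 sets the primary objective as the role of vitamin D "in controlling and reducing DM risks (as measured by HbA1c"), each source being set against the wait list. On the arms, section 3.2 states: "Eligible participants will be randomised in equal proportion into 4 groups: vitamin D supplement, dietary intervention, sun exposure and wait list control".

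On the analysis, section 8 summarises data as means and SDs and says that "two-factor repeated-measures analysis of variance (ANOVA) with a Bonferroni correction will be used in the current trial", with time and intervention as the factors. If the interaction is significant, Tukey comparisons among the four groups follow at 3 and at 9 months. The family to which the Bonferroni correction applies is not stated.

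**The concern.** The calculation and the planned test differ in two respects.

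1. **Endpoint.** The calculation is for a binary event with rates of 35% and 70%. The protocol gives no HbA1c threshold, no definition of response and no comparison of proportions. The planned analysis is of a continuous measure.
2. **Error rate.** The calculation is for one pair of arms at an unadjusted 0.05. The planned comparisons are among four arms, with Bonferroni and Tukey both named.

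The 80% figure is the only justification given for the number recruited, and it appears three times. A reader would take it as the trial's power for its primary objective. The protocol states no HbA1c difference that the trial is designed to detect, so a null result could not be set against one. This matters here because the background section reports that the investigators' own review of sixteen randomised trials did not support the association.

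**Working it through.** **Inputs from the protocol:** rates 0.35 and 0.70, multiplier 7.849, 28 per group, four equal groups, 31-34 recruited per group. The multiplier is (1.960 + 0.842)² = 7.849, so the calculation is two-sided with no adjustment.

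**1. Reproducing the stated figure.**
m = 7.849 × (0.35×0.65 + 0.70×0.30) / 0.35² = 7.849 × 0.4375 / 0.1225 = 28.03.
This agrees with the stated 28, and 4 × 28 = 112.

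**2. Same rates, with the named multiplicity correction (illustration only, since no test of proportions is planned).**
Power = Φ(0.35 / √(0.4375/n) − c). At n = 28 the first term is 2.80. The Tukey critical value for four groups on the normal scale is 2.569.

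| n per arm | First term | Critical value c | Power |
|---|---|---|---|
| 28 | 2.80 | 1.960 (unadjusted) | 80% |
| 28 | 2.80 | 2.569 (Tukey) | 59% |
| 31 | 2.95 | 2.569 (Tukey) | 65% |
| 34 | 3.09 | 2.569 (Tukey) | 70% |

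The last two rows assume that everyone recruited is analysed, as the planned last-observation-carried-forward rule would allow, and that carrying values forward does not dilute the effect. Bonferroni is not tabulated because its family is not stated. If it were the six pairs (assumption), power at 28 per arm would be 56%.

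**3. Means at a single time point.**
For a standardised difference d, the noncentrality is d × √(28/2) = 3.742d.

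- Unadjusted two-sample t test (54 df, critical value 2.005): 80% power at d = 0.76.
- Tukey, four groups (108 df, critical value 2.609): 80% power at d = 0.92. A normal approximation gives (2.609 + 0.842) / 3.742 = 0.92.
- At d = 0.76, power under Tukey is 60%. At d = 0.5, it is 45% unadjusted and 23% under Tukey.

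The protocol gives no HbA1c SD. For assumed SDs of 0.5, 1.0 and 1.5 percentage points, the Tukey figure of 0.92 SD is 0.46, 0.92 and 1.39 points.

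**4. Change from baseline.**
The detectable difference is multiplied by √(2(1−r)), where r is the within-person correlation, also not given. With assumed values of r:

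- r = 0.3: 0.92 × 1.18 = 1.09 SD
- r = 0.5: 0.92 × 1.00 = 0.92 SD
- r = 0.7: 0.92 × 0.775 = about 0.72 SD

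**5. Not computable.** The interaction test that must be significant before any Tukey comparison needs the HbA1c SD, the correlations and the pattern of group means over time. None of these is given.

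**The case against.** The strongest objection concerns a reading that a reader might well infer: that the trial is underpowered, or lacks 80% power. The protocol does not support that. With no SD, target difference or correlation for HbA1c, power for the planned analysis is unknown; it is not shown to be below 80%. If 35% v 70% were a cut on a normally distributed outcome (assumption), the implied difference would be 0.524 + 0.385 = 0.91 SD. Power at 28 per arm would then be 92% unadjusted and about 78% under Tukey, close to the stated figure. A high baseline correlation would help further. This objection stands and limits the conclusion. It does not rescue the claim, because the protocol neither defines such a cut nor states an effect of that size.

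A second objection is that the 59-70% figures belong to a test that nobody plans. That is also correct. They show what the named correction costs on the plan's own inputs and are not the trial's power.

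A third is that a separate analysis plan may hold the detail. It could define a responder or name the primary time point. It could not make this calculation describe an ANOVA on means, and the protocol itself states the power figure, its inputs, the endpoint and the test.

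Nor is this an arithmetic error: the formula gives 28.03 as claimed.

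**Conclusion.** The sample-size basis and the planned analysis do not match. The 80% holds for one unadjusted two-sided comparison of 35% with 70% on an undefined event. It does not apply to the HbA1c analysis in section 8 and is not shown for it.

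The size of the gap can only be illustrated: 80% falls to about 59% at the Tukey critical value on the plan's own rates, or to 65-70% if all recruited participants are analysed. For a single-time-point comparison of means, the detectable difference rises from 0.76 to 0.92 SD. The figures for means assume 28 evaluable per arm, a common SD and a pairwise contrast. The conclusion about mismatch needs none of these assumptions. It does not extend to saying that power for HbA1c is below 80%, nor to which time point should be primary; the protocol names none.

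**What to change.** In the Synopsis, section 3.3 and section 8, replace the 35%/70% calculation with one for HbA1c that states:

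- the SD and its source, with the within-person correlation if change from baseline is analysed;
- the time point and the comparisons that the sponsor designates as primary;
- the multiplicity adjustment and the family it covers.

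Keep the planned size. State the resulting power for a named HbA1c difference, or the difference detectable at 80% power with 28 evaluable per arm. Delete the 80% claim tied to the undefined rates.

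The cost is one paragraph rewritten in three places and probably a less favourable stated figure. No extra participants are needed to correct the statement.

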The vitamin D supplement group will be given an oral vitamin D supplement to ingest, dosage set as 500 IU per day. The dietary intervention group will be asked to follow a 'vitamin D food resources' list to obtain 10-15 μ g/d of vitamin D from food. The sun exposure group will be required to expose about 15% of body surface (hands, face and arms) to natural sunlight anytime from 10am to 4pm for 3-4 minutes/d from December to January, or 8 minutes/d from July to August or 10— 11 min/d from February to June or September to November, to get approximately 12.5 μ g/d of vitamin D per day. No interventions will be given to the wait list control group.

The total study period of the trial is 9 months. A face-to-face adherence reminder and examination session will occur at baseline and on a monthly basis. A blood test of vitamin D level and DM biomarkers will be obtained at baseline, and at the 3rd month and 9th month session. Participants who report with any side effects or upset symptoms will be assessed by study therapists and excluded from the trial once being confirmed.

Statistical considerations

Sample size calculation: By setting the significance level α =0.05, the power 1- β = 0.8 based on Campbell & Machin (1993) formula: m=(Z α + Z2 β)2{ π 1(1- π 1)+ π 2(1- π 2)}/ δ 2, (Z α + Z2 β)2 = 7.849, δ = π 2- π 1=0.7-0.35= 0.35; m=28. Therefore for the current study, the sample size of each group is calculated as at least 28, hence it requires at least 112 participants in total. With the consideration of a dropout rate 10%-20%, it is planned to recruit 31-34 participants per group with 123-134 participants in total.

Analysis plan: Data are expressed as means ± SDs. Initially, the Kolmogorov–Smirnov goodness-of-fit test will be used to assess the normal distribution of variables. Secondly, two-factor repeated-measures analysis of variance (ANOVA) will be used with Bonferroni correction in the current trial with time stages and

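### Each active-versus-wait-list comparison of HbA1c must first pass a group-by-time interaction test and is then one of six Tukey pairs at two visits, which costs power but does not bias the result

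*Protocol*

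**What the plan says.** Section 8 gives one between-group method for all outcomes, and the Synopsis repeats it. The Synopsis wording is "two-factor repeated-measures analysis of variance (ANOVA) will be used with Bonferroni correction in the current trial", with time and intervention as the two factors. Tukey's procedure follows, in Section 8's words, "to identify the differences between four intervention groups at 3 months and 9 months in the case of significant interaction finding in ANOVA". Section 8 does not mention HbA1c, but no other between-group test is described, so this one has to serve the primary outcome.

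Section 2.1 sets the primary objective: supplement, sun exposure and "dietary intervention compare to wait list control", measured by HbA1c. Differences between vitamin D sources are a secondary objective (Section 2.2). Blood is taken at baseline, month 3 and month 9 (Synopsis; Section 5.2).

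The sample size rests on a single comparison of two proportions at 5%: "δ = π 2- π 1=0.7-0.35= 0.35; therefore m=28".

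Three things are left unstated: which visit is primary, whether the follow-up comparisons use raw, change or baseline-adjusted values, and which tests the Bonferroni correction covers.

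**The concern.** The primary question is three differences from control. The planned route adds hurdles that do not belong to that question.

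- No pairwise comparison is made unless an omnibus interaction is significant. With four arms and three time points that is a test on (4−1)×(3−1) = 6 degrees of freedom.
- Tukey on four groups covers 4×3/2 = 6 pairs, of which only 3 are in the primary objective. The critical value is set for all six.
- The comparisons are made at two visits with no order of priority.
- Nothing says that a participant's own baseline HbA1c sharpens the comparison at month 3 or month 9.

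An active arm could therefore differ clearly from control and still not be declared. The sample size has no slack to absorb this, because it was set for one unadjusted pair.

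**Working it through.** **The plan's own figure.** m = 7.849 × (0.35×0.65 + 0.70×0.30) / 0.35² = 7.849 × 0.4375 / 0.1225 = 28.03, which matches the stated 28. Then 4 × 28 = 112. The recruitment range is 112 × 1.1 = 123 to 112 × 1.2 = 134. The formula allows for neither a gate nor multiplicity.

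**Assumptions, because the protocol gives no HbA1c SD, difference or correlation.**
- 28 analysed per arm and SD = 1.
- Compound-symmetric correlation ρ between visits of 0.3 to 0.8.
- The same effect in all three active arms: 0.762 SD at month 9 and half that at month 3. About 0.76 SD is what 28 per arm detects with 80% power in one unadjusted pair.
- Baseline, month 3 and month 9 as the levels of time.

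**Critical values (t, 108 df).** Unadjusted 1.982, Dunnett for three contrasts 2.383, Tukey for four groups 2.609.

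**Approximate power of the month-9 step alone.** The noncentrality is the standardised effect × √(28/2) = effect × 3.742. Power is about Φ(noncentrality − critical value).

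- *Tukey, raw values:* 0.762 × 3.742 = 2.851, and Φ(2.851 − 2.609) = 60% at every ρ. On the same raw values Dunnett gives Φ(2.851 − 2.383) = 68%.
- *Tukey, change from baseline:* divide 2.851 by √(2(1−ρ)). This gives 2.410, 2.851, 3.681 and 4.508, so power is 42, 60, 86 and 97%.
- *ANCOVA with Dunnett:* divide 2.851 by √(1−ρ²). This gives 2.989, 3.292, 3.992 and 4.752, so power is 73, 82, 95 and 99%.

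**With the gate, by simulation.** Power for one named active-versus-control comparison at month 9:

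| Route | ρ=0.3 | ρ=0.5 | ρ=0.7 | ρ=0.8 |
|---|---|---|---|---|
| Gate, then Tukey on raw month-9 values | 40% | 48% | 56% | 60% |
| Gate, then Tukey on change from baseline | 37% | 55% | 83% | 97% |
| ANCOVA with Dunnett, no gate | 73% | 81% | 94% | 99% |

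The familywise error of the ANCOVA route under the null is 5%.

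**Where the loss arises.**
- On raw values the gate costs 60 − 40 = 20 points at ρ = 0.3, 60 − 48 = 12 at 0.5, about 4 at 0.7 and none at 0.8.
- On change from baseline it costs about 5, 5, 3 and 0 points (42 − 37, 60 − 55, 86 − 83, 97 − 97).
- At ρ = 0.7 the raw-value loss is 94 − 56 = 38 points. The gate takes about 4, and using Tukey instead of Dunnett within ANCOVA takes about 3 or 4 (94% to 90%). The remaining 30 or so come from not using baseline.
- At ρ = 0.8 nearly all of the 99 − 60 = 39 points come from not using baseline.

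**Sensitivity.**
- With an effect of 0.75 SD at both visits, gate plus Tukey on raw values gives 44, 50, 57 and 57%, against 71, 80, 94 and 99% for ANCOVA with Dunnett.
- With 0.5 SD at both visits, the ranges are 10–21% and 34–77%.
- If time means months 3 and 9 only, an effect equal at both visits produces no interaction. The gate then passes about 5% of the time, its false-positive rate, and gate plus Tukey gives about 3%.

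**The case against.** The strongest reply is that this is a conventional and mostly conservative analysis, and that the large loss depends on a reading the text does not fix. That is largely right, and it rules out several stronger inferences that a reader might draw.

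- *The follow-up comparisons are certainly on unadjusted values.* Section 8 does not say so. On change from baseline, the shortfall against ANCOVA with Dunnett is 94 − 83 = 11 points at ρ = 0.7 and 99 − 97 = 2 at ρ = 0.8. Baseline adjustment may also be settled in an analysis plan that is not at hand.
- *Baseline is ignored.* If baseline is a level of time, the interaction test uses it, which is why the gate passes more often as ρ rises. Only the comparisons after the gate may leave it out.
- *The gate and the six pairs are the main cause.* At ρ of 0.7 or more they are a minor part. The half-effect pattern at month 3 also disfavours the gate: at ρ = 0.5 it passes about 73% of the time there, against about 85% with a constant 0.75 SD effect.
- *Comparisons are corrected twice.* Bonferroni is attached to the ANOVA and Tukey to the group comparisons. They may serve different tests. The defect is ambiguity, not demonstrated double correction.
- *Error is uncontrolled over two visits.* A 5% gate limits familywise error when no arm has any effect. What remains open is the case where some arms or visits have an effect and others do not.
- *Half the pairs are unnecessary.* The active-versus-active pairs answer the secondary objective. They should stay, but outside the primary family.

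What the reply does not remove: the gate, the four-group Tukey comparison and the two unranked visits are stated in the protocol, so they are not matters merely left to a later document. At ρ of 0.5 or less the planned route falls well short on either reading.

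**Conclusion.** The point holds as a loss of efficiency and a mismatch between test and objective, not as bias or invalidity. Under the stated assumptions the planned route loses 33 to 39 points of power for one active-versus-control comparison if Tukey uses raw values (73−40, 81−48, 94−56, 99−60). It loses 36, 26, 11 and 2 points at ρ = 0.3, 0.5, 0.7 and 0.8 if Tukey uses change from baseline.

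The direction is the same at every correlation tried. The size is not established by the protocol, because effect, SD and correlation are all assumed. Reading time as months 3 and 9 only would make matters much worse for an effect that is constant over both visits.

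Severity: should-fix. A reader might infer that the trial cannot answer its question as planned, but the documents do not support that.

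**What to change.** In Section 8 and the Synopsis:

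1. Name one primary visit for HbA1c, for example month 9, the end of the intervention.
2. Test the three active-versus-wait-list differences at that visit directly, from a model adjusted for baseline HbA1c (ANCOVA, or the equivalent contrasts of a mixed model), with Dunnett or Holm control at 5%.
3. Remove the significant interaction as a precondition. It can still be reported descriptively.
4. Delete the Bonferroni step, or name the set of tests it covers.
5. Report month 3 and the active-versus-active pairs (Tukey) as secondary, in line with Section 2.2.

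The cost is wording only. No extra participants, visits or assays are needed, because baseline HbA1c is already collected. The small downside is that month 3 and the source-versus-source comparisons become secondary. If a separate analysis plan exists, it should carry the same text.

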interventions as factors. A Tukey's post-hoc comparison will be applied to identify the differences between four intervention groups at 3 months and 9 months in the case of significant interaction findings in the ANOVA. Thirdly, correlations between variables were evaluated by using either Pearson (r) (for data with normal distribution) or Spearman (rs) (for data with no normal distribution) correlations. A p-value <0.05 is considered statistically significant. All statistical analyses will be computed using the Statistical Package for Social Science version 17 (SPSS, Chicago, IL, USA). Missing values are treated according to the last observation carried forward (LOCF) method and will be assessed via a sensitivity analysis.

Study duration

The whole study period including research preparation, participants recruitment, intervention, report writing is designed as 3 years; participants are required to be involved in current research for 9 months.

1.	BACKGROUND	6
1.1.	DISEASE BACKGROUND*	6
1.2.	RATIONALE FOR PERFORMING THE STUDY*	6
2.	STUDY OBJECTIVES*	6
2.1.	Primary Objective*	6
2.2.	SECONDARY OBJECTIVES	7
3.	STUDY DESIGN*	7
3.1.	Design*	7
3.2.	STUDY GROUPS	7
3.3.	NUMBER OF PARTICIPANTS*	7
3.4.	NUMBER OF CENTRES	7
3.5.	DURATION	7
4.	PARTICIPANT SECTION	7
4.1.	Inclusion Criteria*	7
4.2.	EXCLUSION CRITERIA*	7
5.	STUDY OUTLINE*	7
5.1.	STUDY FLOW CHART	7
5.2.	Investigation Plan*	9
5.3.	STUDY PROCEDURE RISKS*	11
5.4.	RECRUITMENT AND SCREENING*	11
5.5.	Informed Consent Process*	11
5.6.	ENROLMENT PROCEDURE*	11
5.7.	RANDOMISATION PROCEDURE	11
6.	SAFETY*	12
6.1.	Adverse Event Reporting*	12
6.2.	EARLY TERMINATION	12
7.	BLINIDING AND UNBLINDING	12
8.	STATISTICAL CONSIDERATIONS*	12
9.	CONFIDENTIALITY AND STORAGE AND ARCHIVING OF STUDY DOCUMENTS*	13
10.	OTHER STUDY DOCUMENTS	13
11.	REFERENCES*	14

Version IV; November2018

1.BACKGROUND

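### LOCF is the main rule for missing HbA1c, so 3-month or baseline values stand in for missing 9-month values and bias the 9-month contrasts in a direction that cannot be known in advance

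*Protocol*

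**What the plan says.** The rule appears twice. Section 8 has "Missing values are to be treated according to the last observation carried forward (LOCF) method and will be assessed via sensitivity analysis", and the Synopsis analysis plan has "Missing values are treated according to the last observation carried forward (LOCF) method and will be assessed via a sensitivity analysis". Neither place limits the rule to particular variables, so it covers HbA1c, which Section 2.1 names as the measure for the primary objective.

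The Synopsis fixes the laboratory schedule: "A blood test of vitamin D level and DM biomarkers will be obtained at baseline, and at the 3rd month and 9th month session". Section 5.2 agrees; the other monthly visits have no blood test.

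The filled data go into the main analysis, where "two-factor repeated-measures analysis of variance (ANOVA) with a Bonferroni correction will be used in the current trial with time stages and interventions as factors". If the interaction is significant, "Tukey's post-hoc comparison will be applied to identify the differences between four intervention groups at 3 months and 9 months".

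Sections 3.3 and 8 plan for 10% to 20% dropout. Sections 5.3 and 6.1 say that participants who report adverse effects leave the trial, and they anticipate food intolerance or allergy in the dietary arm.

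**The concern.** With only three blood tests there is little to carry forward. A participant lost after month 3 is given a value six months old. One lost before month 3 is given a value nine months old, and so a change of exactly zero. Participants are recently diagnosed and on no diabetic medication or insulin at entry (Section 4.1), and the protocol offers no reason to expect their HbA1c to stay flat.

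At stake is the 9-month comparison of the three interventions with the wait-list control. LOCF shifts it by an amount that depends on who leaves each arm, when they leave, and how HbA1c moves meanwhile. The filled values also count as full observations, so the trial appears more precise than the data collected allow.

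**Working it through.** **The plan's own figures.** The protocol gives no figure for the effect of LOCF. Its sample size does not depend on LOCF but supplies the arm sizes: 7.849 × (0.35 × 0.65 + 0.70 × 0.30) / 0.35² = 7.849 × 0.4375 / 0.1225 = 28.03, stated as 28. Then 28 × 1.1 = 30.8 and 28 × 1.2 = 33.6 give the stated 31 to 34 per group.

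**Inputs from the protocol.** Dropout d = 0.10 or 0.20; blood tests at months 0, 3 and 9; 31 or 34 per arm.

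**Assumptions (not in the protocol).** s = share of losses before month 3; r = 3-month effect divided by 9-month effect; HbA1c SD of 1 at every visit; correlation 0.7 between visits; losses completely at random within arm.

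**Step 1: equal loss in both arms.** Those observed at month 9 show the full effect, those lost late show r times it, and those lost early show none:

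share kept = (1 − d) + d × (1 − s) × r

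| d | s | r | Share kept |
|---|---|---|---|
| 0.20 | 1 | any | 0.80 |
| 0.20 | 0.5 | 0.5 | 0.80 + 0.20 × 0.5 × 0.5 = 0.85 |
| 0.20 | 0 | 1 | 1.00 |
| 0.10 | 1 | any | 0.90 |
| 0.10 | 0.5 | 0.5 | 0.90 + 0.10 × 0.5 × 0.5 = 0.925 |
| 0.10 | 0 | 1 | 1.00 |

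For r between 0 and 1 the range is 80% to 100% at 20% dropout and 90% to 100% at 10%.

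**Step 2: waning effect.** Take 0.60 SD at month 3 and 0.30 SD at month 9, with 20% lost, all after month 3. LOCF expects 0.80 × 0.30 + 0.20 × 0.60 = 0.36 SD, an overstatement of about 20% (0.358 in simulation, 19%).

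**Step 3: no true effect, unequal loss, drifting HbA1c.** Let HbA1c rise by 0.25 SD at month 3 and 0.75 SD at month 9 in both arms, with half the losses early.

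- Control, 10% lost: 0.90 × 0.75 + 0.05 × 0.25 = 0.6875.
- Active, 20% lost: 0.80 × 0.75 + 0.10 × 0.25 = 0.625. The false benefit is 0.06 SD; simulated type I error about 6%.
- Active, 30% lost: 0.70 × 0.75 + 0.15 × 0.25 = 0.5625. The false benefit is 0.125 SD; simulated type I error about 10%. A 30% loss lies above the protocol's range.

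With the 20% versus 10% loss and a true effect of 0.25 SD at month 3 and 0.50 SD at month 9, the two biases nearly cancel (0.487 simulated).

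**Step 4: standard error.** A two-arm contrast of change from baseline to month 9 was simulated 20,000 times per scenario, with equal loss, half of it early, and a true effect of 0.25 SD at month 3 and 0.50 SD at month 9.

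| | Estimate | SE | 95% coverage |
|---|---|---|---|
| 20% loss, 34 per arm: no data missing | 0.500 | 0.187 | 95.1% |
| 20% loss: LOCF | 0.424 | 0.180 | 92.6% |
| 20% loss: observed at month 9 only | 0.498 | 0.210 | 94.7% |
| 10% loss, 31 per arm: LOCF | 0.463 | 0.192 | 94.5% |
| 10% loss: observed at month 9 only | 0.501 | 0.207 | 95.0% |

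The LOCF standard error is 14% below the observed-data one at 20% loss (0.180 / 0.210 = 0.857) and 7% below at 10% (0.192 / 0.207 = 0.928). At 20% loss it is even below the value with nothing missing, because a baseline carried forward adds a change of zero with no spread. It does match the spread of the LOCF estimate itself (0.180 against 0.181).

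These runs use a simple two-arm contrast, not the four-arm ANOVA. The observed-only rows are a benchmark under random loss, not a forecast for a mixed model.

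**The case against.** Much of the case for leaving the rule alone has substance.

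- **LOCF is conservative.** A reader might infer that LOCF shrinks the effect and so is safe in a superiority trial. That needs similar loss across arms and an effect that is stable or growing. Steps 2 and 3 show that neither shrinkage nor safety is general.
- **Dropout will differ by arm.** The documents do not support this as a certainty. Sections 5.3, 6.1 and 6.2 call adverse effects unlikely, Section 6.2 mentions clearance of allergy history at screening, and exclusion for adverse effects is not confined to the dietary arm. Loss may differ by arm; no more can be said. The protocol also does not say whether excluded participants stay in the analysis, so filling their values is inferred from the unrestricted rule.
- **The standard error is simply wrong.** This too goes further than the check allows, since it describes the LOCF estimate correctly. Bias explains nearly all the lost coverage: 0.076 / 0.180 is a shift of about 0.42 standard errors, which alone gives about 93%.
- **A sensitivity analysis is promised.** It is, and its details may properly sit in an SAP that is not at hand, so their absence is no fault. But the same sentence keeps LOCF as the main rule whatever the sensitivity analysis shows.
- **The harm is modest.** At 10% equal loss it is: coverage is 94.5%. It grows with the amount and imbalance of loss.

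**Conclusion.** The concern holds as one of bias of unknown direction. The protocol itself fixes LOCF as the main rule, and the three-test schedule means that 3-month or baseline values replace missing 9-month HbA1c.

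Under equal loss and a 3-month effect no larger than the 9-month effect, 80% to 100% of the effect is kept at 20% dropout and 90% to 100% at 10%; the middle cases are 85% and 92.5%. Outside those conditions LOCF can overstate an effect, by about a fifth in the waning example, or produce a false one, of 0.06 SD with 20% versus 10% loss.

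The standard error understates uncertainty about the true 9-month effect, by 7% to 14% against the observed-data benchmark in the scenarios tried. All sizes rest on the assumed timing of loss, course of effect, SD and correlation. The existence of the bias needs only missing 9-month values and an HbA1c contrast or level that moves between visits.

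**What to change.** In Section 8 and the Synopsis, replace LOCF as the main rule with a likelihood-based mixed model for repeated measures on all observed HbA1c values. Include baseline as a response constrained equal across arms, with terms for visit and arm by post-baseline visit and an unstructured covariance. With baseline as a response, every randomised participant who has a baseline value contributes. If baseline were only a covariate, anyone lost before month 3 would drop out of the model. The constraint relies on baseline blood being drawn before the intervention starts. Multiple imputation is an acceptable alternative.

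Keep LOCF at most as a sensitivity analysis, beside a delta-adjusted analysis that allows data to be missing not at random.

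The cost is revised wording, slightly more analysis work, reliance on a missing-at-random assumption in the main analysis, and a somewhat larger but more honest standard error. No new data are needed.
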